**FORM: Application for Human Research**

NUMBER	FORM DATE	PAGE
F200		5 of 18

SECTION 2: GENERAL INFORMATION

1. Not including this project submission, how many:
 - a. Human Research studies is the PI involved in as key personnel? 6
 - b. Active subjects are there in the PI's open Human Research study/ies? 21 (61 total)
 - c. Investigators are involved on the PI's open Human Research studies? 21
 - d. Research coordinators are involved on the PI's open Human Research studies? 1
2. What is the expected length of this project? 3 years
3. Retention of study materials before, during, and after completion of the project:
 - a. Where will the original signed consent and PHI Authorization documents be stored (building name and room)? Biomedical Research Labs (BRL) room B101
 - b. How long will the data/consents be kept after conclusion of the project? 6 years Other: _____
4. If the Human Research project is funded, identify all sponsoring entity/ies): Guided Therapy Systems
5. If funding support is from a federal agency (such as a training grant, infrastructure grant, salary support, project grant, etc.), list federal agency and grant number
6. Total funding amount **OR** per subject amount: _____
7. The Principal Investigator hereby affirms that ALL individuals who meet the definition of "investigator" for this project in the current "Policy on Investigator Conflict of Interest in Research" have completed the mandatory Conflict of Interest training (<http://www.orcr.arizona.edu/coi/training>) Yes
8. Will this project be registered on ClinicalTrials.gov because ...?
 - a. the local PI is the sponsor of the clinical trial (including NIH-funded clinical trials where the local PI is the funding recipient OR IND holder);
OR
 - b. The PI has been designated by a sponsor, contractor, grantee, or awardee to register the clinical trial to ClinicalTrials.gov, as the Responsible Party (responsible for conducting the trial, and has sufficient data rights)
If yes, please check the appropriate box:
 ClinicalTrials.gov "NCT" number for this trial (define):
 Registration pending

**FORM: Application for Human Research**

NUMBER	FORM DATE	PAGE
F200		6 of 18

Clinical trial does not require registration (click above to see what studies qualify)

SECTION 3. PROJECT NARRATIVE**1) Background**

The primary objective of this study is to evaluate the efficacy of combining intense therapeutic ultrasound (ITU) with standard care for the treatment of chronic plantar fasciitis. A secondary objective is to evaluate the tolerability and safety of intense therapeutic ultrasound in the treatment of plantar fasciitis.

These objectives will be accomplished through the following specific aims:

Aim # 1: Compare patient reported outcomes of pain, function and level of activity for subjects treated with standard of care plus ITU (ITU group) to those treated with standard of care plus sham ITU (control group).

Aim # 2: Compare the changes in plantar fascia thickness in subjects treated with standard of care plus ITU to those treated with standard of care plus sham ITU.

Aim # 3: Evaluate the tolerability and safety of ITU for the treatment of chronic plantar fasciitis Chronic Plantar Fasciitis. Chronic plantar fasciitis (CPF) is a common cause of plantar heel pain that is a result of a degenerative process of the plantar fascia and its surrounding perifascial structures. It is the most common cause of heel pain, affecting 10% of the U.S. population, and one of the most common foot and ankle problems. One study showed that individuals with this disease scored significantly lower in general health-related quality of life in addition to foot specific quality of life (pain and function).

The plantar fascia, or plantar aponeurosis, originates on the posterior tuberosity of the calcaneus and inserts into the proximal phalanges of the toes. It acts like a cable, which tightens with flexion of the metatarsophalangeal joints, the “windlass” mechanism, thereby restoring the arch during mid-stance, stiffening the medial column of foot for push-off and transferring the force of the gastrocnemius muscle contracture to the ground. Although the exact etiology of CPF is unclear, the predominance of evidence indicates that it is the combination of age and overuse which lead to degenerative changes within the fascia that result in the symptoms associated with this disease. The most common presentation for patients with plantar fasciitis include pain with the first few steps in the morning, pain at the beginning of the activity that resolves with continued activity, pain and stiffness with prolonged standing, and pain at the end of the day.

The diagnosis of CPF is made clinically based on history and physical exam. Confirmation with diagnostic imaging may be necessary when the symptoms are atypical or are refractory to treatment. MRI is a useful diagnostic tool to evaluate for plantar fascia thickening and edema in and around the fascia, both of which are consistent with the diagnosis of CPF. In addition, many physicians use MRI to exclude other causes of plantar heel pain. Ultrasound can also be used to measure the thickness of the plantar fascia. Multiple studies have shown that patients with CPF have increased thickness of the fascia compared to asymptomatic individuals. Mean thickness in these studies for subjects with CPF range from 4.8-6.5 mm as opposed to 2.3-4.0 mm for subjects without the disease. One of the studies showed that the thickness was increased in medial, central and lateral bands of plantar

**FORM: Application for Human Research**

NUMBER	FORM DATE	PAGE
F200		7 of 18

fascia uniformly along with 68% of patients with CPF reporting central band tenderness as opposed to 26% having lateral band tenderness. In addition to the evidence of inflammation, the presence of a hyper-echoic lesion in the plantar fascia was noted in 68% to 84% of patients with CPF. Diagnostic ultrasound has also been used to quantify the effectiveness of treatments such as extra-corporeal shock wave therapy, NSAIDs and Botox injections for subjects with CPF.

More than twenty different treatments have been used for plantar fasciitis. The combination of rest, ice, stretching and NSAIDs are used as initial management in most patients and have been shown to effectively treat symptoms in 90% of patients in less than 12 months. However, 10% of patients fail conservative management and continue to have symptoms beyond 12 months (termed refractory plantar fasciitis or RPF). Surgery consisting of partial plantar fascia release or gastrocnemius recession is often considered in these patients. However, the outcomes of surgery are not uniformly positive with 50% of patients reporting residual symptoms. Moreover, evidence supporting surgical treatment of RPF is weak as there are no randomized controlled trials comparing its efficacy to other treatments. Thus, for many patients the risks of surgery such as arch instability, prolonged wound healing, and longer rehabilitation times simply outweigh the benefits. Is there a non-invasive treatment that can be used as an adjunct to speed healing in patients with CPF and as an alternative to surgery in those with RPF? The primary objective of this study is to evaluate the efficacy of combining the non-invasive treatment with intense therapeutic ultrasound (ITU) with standard care for the treatment of chronic plantar fasciitis. A secondary objective is to evaluate the tolerability and safety of intense therapeutic ultrasound in the treatment of plantar fasciitis.

Intense therapeutic ultrasound (ITU). Various types of ultrasound have been used to treat soft tissue injuries since the 1930s. Intense therapeutic ultrasound (ITU) is a recently developed ultrasound based therapy in which sound waves are concentrated to produce selective thermal coagulative change over a small area while leaving the remaining regions unaffected. ITU has been used clinically for treating the facial skin for the past decade and it has recently received FDA approvals for non-surgical brow and submental tissue lifting. Over 300,000 patients worldwide have been treated using this technology. Clinical studies have shown that 85% of subjects receiving this treatment on facial skin tissue showed an improvement in facial lifting with no significant pain, erythema, inflammation or scarring. Histologically, it has been shown that ITU induces the production of dermal collagen with thickening of the dermis and straightening of the elastic fibers in the reticular dermis. On-going research in our laboratory has shown that ITU can improve healing of damaged Achilles tendon in a rabbit model. Preliminary results showed an increase in markers for wound healing (e.g. VEGFa, TNF α , IL-1 β , and TGF β 1) and a decrease in markers for scar tissue formation (e.g. COL1 α 1, COL1 α 2, and COL2 α 2) in injured rabbit tendon treated with ITU compared to injured, untreated rabbit tendon. These results have led us to want to explore the possibility using ITU to treat patients with CPF.

2) Lay Summary (approximately 400 words)

The purpose of this study is to assess the effectiveness of ITU in the treatment of CPF by comparing pain, function, and change in plantar fascia thickness in subjects treated with ITU in addition to standard of care to subjects that are treated with standard of care alone. The primary outcome measure will be a computer adaptive questionnaire where pain, function and level of activity will be compared between the two groups. In addition, with the use of diagnostic ultrasound, plantar fascia thickness and presence or absence of hyper-echoic lesion will be compared between the two groups. Finally, the safety and tolerability of ITU will be monitored through the course of the study. It is hypothesized that patients receiving ITU in addition to standard of care will have a more rapid resolution of their pain, faster return to activities, and a greater decrease in plantar fascia thickening on ultrasound as compared to those only receiving standard of care.

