**FORM: Application for Human Research**

NUMBER	FORM DATE	PAGE
F200		11 of 18

patient reported outcome measures assessing pain, function and level of activity. Subjects will complete validated patient reported outcome questionnaires assessing pain, function and level of activity prior to initiating treatment and at 0, 2, 4, 6, 12, and 24 weeks after starting treatment.

Pain will be assessed using the of the foot function index pain subscale (FFI-P) and the subject reported outcome measures (SROM). These two instruments have been used to assess pain in previous studies of plantar fascia treatments. (Please see Appendices 1-D and 1-E of the Protocol.)

Function will be assessed using two validated PRO instruments the PROMIS PF CAT and the FAAM. The PROMIS PFCAT is a subject relevant outcome measure that uses computer adaptive survey questions to assess the patient's pain and function in relation to daily activities. (Please see Appendix 1-A of the Protocol.) The FAAM has been shown to be a reliable, responsive, and valid measure of physical function for individuals with a broad range of musculoskeletal disorders of the lower leg, foot, and ankle. (Please see Appendix 1-B of the Protocol.)

Level of Activity will be assessed using the activity subscale of FAAM. This subscale scores quantitatively the level of difficulty subjects often face when they perform basic activities of daily living. It has shown to be an accurate and reliable predictor of the activity level while performing day-to-day activities. (Please see Appendix 1-B of the Protocol.)

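### The declared primary outcome, one unnamed adaptive questionnaire covering pain, function and activity, does not isolate pain, and no single primary measure binds the protocol and the SAP

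*Protocol*

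**What the plan says.** Protocol, Section 3, item 2 (Lay Summary) declares the primary outcome: "The primary outcome measure will be a computer adaptive questionnaire where pain, function and level of activity will be compared between the two groups". It does not name the questionnaire or give a score or time point. The hypothesis in the same paragraph is that patients given ITU "will have a more rapid resolution of their pain, faster return to activities, and a greater decrease in plantar fascia thickening on ultrasound".

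Aim 1 in item 1 (Background) covers the same three domains without ranking them: "Compare patient reported outcomes of pain, function and level of activity for subjects treated with standard of care plus ITU".

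Item 7, under Patient Reported Outcome Measures (Aim 1), assigns the instruments by domain:

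- Pain: the "foot function index pain subscale (FFI-P) and the subject reported outcome measures (SROM").
- Function: "Function will be assessed using two validated PRO instruments the PROMIS PF CAT and the FAAM".
- Activity: "Level of Activity will be assessed using the activity subscale of FAAM".

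The same section says that the PROMIS PFCAT "uses computer adaptive survey questions to assess the patient's pain and function in relation to daily activities". No other instrument is described as adaptive.

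Item 7, under Statistical analysis, lists FFI-P, PFCAT and FAAM together for one comparison, with significance at P<0.05 and no order of priority.

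The SAP (Statistical Approach) covers a 25% pain-reduction goal on a pain scale, hypoechoic lesion volume and the FFI pain subscale. It labels none of them primary and mentions neither the PF CAT nor the FAAM.

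**The concern.** A primary outcome should point to one number per patient. Here it points to one questionnaire that is said to compare three things, while the methods measure those things with four named instruments. The one instrument that fits the adaptive label sits in the function group.

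Two consequences follow. First, a difference on the PF CAT could not be credited to pain specifically, and a null result on it could hide a pain benefit. Second, the documents lead readers to different headline results. Someone following the Lay Summary would judge the trial on the PF CAT. Someone following the protocol's analysis paragraph would have three scores of equal standing. Someone following the SAP would judge it on pain or lesion size. With no binding choice, the headline can be settled after the results are known.

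**Working it through.** The plan has no figure of its own to reproduce. It gives a target of 50 participants, called a pilot, with no power, effect size or SD. The check is mainly a comparison of the texts.

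**Step 1. Where each domain is measured and analysed**

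| Domain | Lay Summary | Aim 1 methods | Protocol analysis | SAP |
|---|---|---|---|---|
| Pain | adaptive questionnaire, primary | FFI-P, SROM | FFI-P | pain scale (25% goal); FFI pain subscale |
| Function | same questionnaire | PROMIS PF CAT, FAAM | PFCAT, FAAM | none |
| Activity | same questionnaire | FAAM activity subscale | FAAM, subscale not separated | none |

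**Step 2. Which instrument the primary means.** Only the PROMIS PF CAT is described as adaptive, so the Lay Summary can only mean that one.

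**Step 3. Whether it yields the three quantities.** The methods file it under function but describe it as assessing pain and function in daily activities. On the first reading it gives no pain score. On the second it gives a score that mixes pain with function. The analysis paragraph treats it as one entry, and no separate pain or activity score is described in the supplied text. On either reading, pain is not isolated.

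**Step 4. Whether later text restores a single primary.** It does not. The protocol's analysis paragraph gives no score priority, and the SAP omits the PF CAT and names no primary.

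**Step 5. Cost of having no priority.** Inputs: three scores (FFI-P, PFCAT, FAAM) and alpha = 0.05, both from the protocol's analysis paragraph. Assumptions: one valid between-group test per score, no true effect on any score, and independence. The chance of at least one false positive is

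1 − (1 − 0.05)^3 = 1 − 0.857 = 0.143.

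The limit under any correlation is 3 × 0.05 = 0.15, and positive correlation brings the figure below 0.143. If the FAAM activity subscale is tested as a fourth score, the result is 1 − 0.95^4 = 0.185 under independence. Testing at several visits would add to this, but the plan does not say how many visits are tested.

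**Step 6. What the two documents share.** Questionnaire scores analysed in the protocol are FFI-P, PFCAT and FAAM. Patient-reported scores in the SAP are the pain scale and the FFI pain subscale. The only common score is the FFI pain subscale. Post-baseline visits are weeks 2, 4, 6, 12 and 24 in the protocol and weeks 4, 8, 12 and 26 in the SAP, so only weeks 4 and 12 are common. Week 12 is the later of these and matches the three-month commitment in the recruitment text.

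**Step 7. Whether the SAP already has the contrast.** It states t-tests of follow-up against baseline and, for FFI, a percentage reduction in the average score. It states no test of ITU against control on FFI.

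**The case against.** A reader might infer that the primary outcome cannot test pain at all because the PF CAT measures physical function only. The documents do not support this. The supplied text never expands the letters PF, and the protocol's own description of the instrument includes pain. Its scoring may also be set out in Appendix 1-A, to which the protocol refers and which was not among the documents supplied. Pain is analysed elsewhere in any case: FFI-P in the protocol, the pain scale and FFI pain subscale in the SAP.

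A reader might also treat pain as the leading hypothesis. It is listed first, but the sentence joins pain, activities and fascia thickness without ranking them. Nor can a loss of power from using a function score be put into figures. Neither document gives an effect size, or the share of a pain effect that would reach the PF CAT, so any such number would be invented.

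It is also fair to say that the Lay Summary is not the operative methods text, that this is a pilot, and that choosing a primary is the sponsor's decision. A single week-12 comparison would not measure how quickly pain resolves, since the arms could differ early and then converge.

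These arguments limit the point without removing it. The Lay Summary is the only text that declares a primary. The operative sections do not replace it, and the SAP does not analyse the instrument it implies.

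**Conclusion.** The point holds as a defect of specification. The declared primary does not isolate the pain effect named in the hypothesis, and no single primary measure governs both documents. It does not follow that the pain hypothesis goes untested.

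The 14.3% in the working is the error rate that unprioritised testing of three scores would allow. It rests on independence and one valid test per score, and it is not an estimate for this trial. The remaining harm, a result credited to the wrong domain or a headline chosen late, cannot be sized from the documents. The point should be corrected; for a 50-person pilot its weight is moderate. Confidence is medium, because the PF CAT appendix was not available.

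**What to change.** In the Lay Summary, the protocol's Statistical analysis paragraph and the SAP, name the same primary score, time point and ITU-versus-control contrast.

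- **Primary.** FFI-P at week 12 is the natural choice, for the reasons in Step 6.
- **SAP test.** Add a between-group test of that score for independent arms, for example the week-12 score adjusted for baseline. This is an added analysis as well as a wording change. The paired t-test named in the protocol should be replaced to match.
- **Secondary outcomes.** List PROMIS PF CAT and the FAAM activity subscale separately, and remove the statement that the adaptive questionnaire compares pain and activity.
- **Speed of response.** Report between-group FFI-P differences at the earlier visits as a supporting time-course analysis, after reconciling the two visit schedules.
- **Alternative.** If the sponsor keeps the PF CAT as primary, the Lay Summary must limit it to what that score measures, and the SAP must analyse it.

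No new data collection is needed, because the protocol already schedules the questionnaires at each of these visits. The downside is that a benefit confined to function becomes a secondary finding. The SAP is written in the past tense, so if data have already been seen, the choice of primary must be declared as post hoc.

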**FORM: Application for Human Research**

NUMBER	FORM DATE	PAGE
F200		9 of 18

to heal will be compared for traditional treatment methods + placebo to that required by traditional treatment + ITU. Every subject will receive anti-inflammatory medication, a viscoelastic heel cup, and physical therapy. Patients receiving just these treatments will be compared to those also receiving ITU treatments. Who can participate? The following criteria are required for participation: A physician associated with the study has diagnosed you with plantar fasciitis. To be eligible you need to have chronic heel pain that is diagnosed as plantar fasciitis by a physician associated with the study. The/your symptoms exist in only one foot. You must not have diabetes or be pregnant. You must be 18 years or older. What will participation require? You will need to be assigned to either a control group (standard medical care) or to an experimental group (standard medical care + ITU). You will need to not use any other treatments. You will need to commit to the assigned treatment for 3 months. You will need to answer an additional online or telephone questionnaire at 6 months. Why should I participate? Although you will not receive payment, what is learned may benefit others! To participate, please call [contact information]. If interested, please call [contact information] or send an email to [contact information] and provide preferred contact information."

In addition to anatomical labeling of the *achilles tendon, calcaneus, and plantar fascia*, we would like to use the captions, "*Inflammation of the plantar fascia can cause heel pain*" and "*stretching the plantar fascia*."

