Randomization and Blinding. Suitable subjects will be randomly assigned (1:1) to receive standard of care with a sham ultrasound treatment (Control group) or standard of care + ITU treatment (ITU group) by the application of an algorithm (e.g. even vs odd) to the number provided by a random-number generator. Most members of the research team and the subject will be blinded to group assignment. Only the clinical research coordinator and ultrasound treatment team will be privy to the subject's group assignment.

Patient Reported Outcome Measures (Aim 1). The principal aim of this study is to compare the efficacy of treatment and time course of response to treatment between the two groups using validated

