Assessment of Safety and Tolerability (Aim 3). Subject self-assessments of treatment tolerability will be conducted immediately after, two days after (phone survey) and two weeks after treatment using a 10-point visual analog scale (VAS, see Appendix 1-C). The subject will be asked to report their current level of pain and the maximum level of pain experienced over the last two days. The VAS is the standard for assessing pain for both clinical and research purposes. Recording of adverse events will take place at all visits (see adverse event reporting form Appendix 4 in the protocol). Adverse events and serious adverse events will be monitored throughout the study. A treatment will not be administered if there is residual pain/discomfort experienced by the subject from the previous treatment.

Statistical analysis. Data will be assessed for variance homogeneity and normality. FFI-P, PFCAT, and FAAM scores before and after intervention will be compared between the two groups using a paired t-test. Additionally, the mean thickness of the plantar fascia will be compared between the two groups before and after treatment and significance determined utilizing paired t tests. P<0.05 is considered to be statistically significant.

8) Risks to subjects

Exposure to ITU may produce short-term sensations which may cause discomfort and mild erythema for up to a few hours following the exposure. No detrimental side effects have been reported in previous clinical trials investigating similar devices in which ultrasound energy was applied to the neck and face. Additionally, the ITU in this investigation will utilize lower power parameters than those reported for these similar devices. We are seeking classification of the GEN II system (Guided

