## Statistical Approach

- Pain Reduction:

Pain level at the plantar fascia was self-reported by subjects at pre-treatment (used as baseline measurement) and again at each follow-up - 4, 8, 12, and 26 weeks - after initial treatment. The pain scale subjects used to identify their level of pain was a 10-point pain scale range, where 0 = no pain, 1 = slight pain through 10 which equates to the patient's worst imaginable pain. The goal for all subjects in the treatment group was to reduce pain by at least 25%. Pain scores reported at follow-up timepoints were compared to baseline score for each subject to determine if the goal was met by dividing the difference in the follow-up and baseline pain score by the baseline pain score. The percentage of subjects that met the pain reduction goal was calculated at each timepoint for both control/sham-treated and treatment groups by dividing the number of subjects that achieved the pain reduction goal at each timepoint by the total number of patients that gave a pain score for that time point.

- Plantar Fascia Hypoechoic Lesion Size:

A large proportion of patients suffering from chronic plantar fasciitis present with hypoechoic lesions in or around the proximal plantar fascia, as viewed by diagnostic ultrasound imaging[7].

Hypoechoic lesions were imaged and volumes were calculated at the baseline visit and each follow-up visit by measuring the inferior-to-superior and posterior-to-anterior radii in the long axis and the medial-to-lateral radius of the transverse axis and applying the following formula for the volume of an ellipse:

$$\text{Volume} = (4/3)\pi \cdot r_1 \cdot r_2 \cdot r_3$$

With  $r_1$ ,  $r_2$ , and  $r_3$  representing the three radii detailed above. Changes to lesion volumes were recorded at each follow-up timepoint and compared to baseline by dividing the volume of the lesion at that timepoint with the volume of the same lesion at pre-treatment baseline.

- Foot Function Index Score Reduction:

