In addition to the 11-point VAS pain scale, patients self-reported answers to questions from the Foot Function Index (FFI) pain subscale questionnaire, which has been standardized in a number of PF-focused publications [8-10]. Scores range from 0-90, with 0 indicating no pain and 90 indicating the worst pain imaginable in a variety of daily activities involving use of the plantar fascia. Self-reported scores were taken at baseline and each follow-up timepoint. The average score for each timepoint were calculated, and follow-up averages were compared to baseline to calculated the percentage reduction in score.

- Statistical Calculations

Student T-tests were utilized to determine statistically significant differences between baseline and subsequent follow-up measurements for self-reported and lesion size measurements. The level of significance ( $\alpha$ ) was set to 0.05.

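### Speed and between-group time course are part of the hypothesis and principal aim, but neither document gives a valid between-arm test of them, and the two visit schedules share only weeks 4 and 12.

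*Protocol*

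**What the plan says.** **Question.** The Lay Summary (Protocol Section 3, item 2) predicts "more rapid resolution of their pain, faster return to activities" with ITU, together with a larger reduction in fascia thickness. Two of the three clauses concern speed and the third concerns size of change. Under Patient Reported Outcome Measures (Aim 1) in item 7, the principal aim is to "compare the efficacy of treatment and time course of response to treatment between the two groups". The recruitment text in item 6 says that the time required "to heal will be compared for traditional treatment methods + placebo to that required by traditional treatment + ITU". The Background (item 1) states the primary objective more broadly, as efficacy of ITU added to standard care.

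**Visits.** Table 1 and the Aim 1 text schedule questionnaires at weeks 0, 2, 4, 6, 12 and 24. The SAP, under Pain Reduction, has pain reported before treatment and "again at each follow-up - 4, 8, 12, and 26 weeks - after initial treatment".

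**Tests.** Protocol item 7, Statistical analysis: "FFI-P, PFCAT, and FAAM scores before and after intervention will be compared between the two groups using a paired t-test". No visit is named. SAP, Statistical Calculations: t-tests for "differences between baseline and subsequent follow-up measurements", at a significance level of 0.05. Under Pain Reduction the SAP also gives, for each arm and timepoint, the percentage of subjects whose pain fell by at least 25%. No test is attached to it.

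**The concern.** A claim that one arm improves sooner is a claim about the difference between arms at early times, so it needs a between-arm estimate with its uncertainty. The only tests that can be run as written compare follow-up with baseline. Both arms receive NSAIDs, heel cups and physical therapy, so a fall from baseline is expected in both whether or not ITU adds anything. A reader of such results may treat a significant change in one arm and a non-significant change in the other as evidence for ITU, which it is not.

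The protocol puts three questionnaire visits in the first six weeks after treatment starts, where a difference in speed would mostly appear. The SAP list keeps only one of them, week 4.

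**Working it through.** The documents give no power, effect size, SD or dropout figure, so there is no stated result to reproduce.

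**1. Visits after baseline**

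| | Weeks |
|---|---|
| Protocol | 2, 4, 6, 12, 24 |
| SAP | 4, 8, 12, 26 |
| In both | 4, 12 |
| Protocol only | 2, 6, 24 |
| SAP only | 8, 26 |

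**2. Planned analyses**

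| Analysis | Compares arms? | Uses time? | Inferential? |
|---|---|---|---|
| Protocol paired t-test | Intended, but pairing does not fit two independent groups | No visit or time term | Yes |
| SAP t-tests | No arm comparison stated | Each follow-up against baseline | Yes |
| SAP 25% responders | Shown side by side | By visit | No |

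Neither document contains a longitudinal model, an arm-by-visit term or a time-to-response analysis.

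**3. Why baseline tests cannot stand in.** Inputs: target enrolment 50 (Study Population) and 1:1 allocation (Randomization and Blinding), so 25 per arm is assumed; two-sided 0.05 is assumed. Suppose the SAP tests are run within each arm (the SAP does not say) and the arms are truly identical. If each within-arm test has power p, exactly one arm is significant with probability 2p(1 − p). With p from the noncentral t on 24 degrees of freedom:

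| Assumed standardized change | p | 2p(1 − p) |
|---|---|---|
| 0.3 | 0.302 | 0.42 |
| 0.4 | 0.484 | 0.50 |
| 0.5 | 0.670 | 0.44 |
| 0.6 | 0.821 | 0.29 |

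**4. Precision of a between-arm analysis.** With 25 per arm and 80% power, a two-sample t-test of scores at one visit detects 0.809 SD (exact t; the normal approximation gives (1.96 + 0.84) × √(2/25) = 0.79). Let r be a common correlation between any two visits, baseline included. Relative to the outcome variance, the variance is:

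- one baseline-adjusted visit: 1 − r²
- baseline-adjusted mean of the three visits at weeks 2, 4 and 6: (1 + 2r)/3 − r²

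The detectable difference is 0.809 × √variance.

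| r (assumed) | One visit | Weeks 2–6 mean | Variance ratio |
|---|---|---|---|
| 0.4 | 0.84, giving 0.74 SD | 0.44, giving 0.54 SD | 0.44/0.84 = 52% |
| 0.7 | 0.51, giving 0.58 SD | 0.31, giving 0.45 SD | 0.31/0.51 = 61% |

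These figures assume no dropout and the same arm difference at all three visits.

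**5. Relaxing the equal-difference assumption.** Take exponential improvement curves with time constants of 2 and 8 weeks, the same final gain of 1 SD, and r = 0.5 (all assumed). The arm difference is 0.41, 0.47 and 0.42 SD at weeks 2, 4 and 6, then 0.22 at week 12 and 0.05 at week 24. Baseline-adjusted power is about 47% at week 4 alone and 65% for the weeks 2–6 mean. Under these curves most of the contrast is early.

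**The case against.** A reader might infer that the trial's main question goes unanswered, or that the hypothesis can be neither confirmed nor refuted. The documents do not support this. The primary objective is efficacy in general, the first specific aim compares pain, function and activity without mentioning time, and one hypothesis clause concerns the size of the thickness change. The protocol does intend to compare the groups, although with an unsuitable test. The SAP does describe response by arm and visit. What is missing is valid inference on time course.

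A reader might also infer that week-2 and week-6 scores exist and were left out. The SAP is written in the past tense and does not say so; those scores may never have been collected under the schedule it reports. It cannot be assumed that they are available to analyse.

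Two technical limits also stand. An early average is a difference in level and cannot separate faster improvement from larger improvement. Table 1 places the second ITU session at week 2, so scores from that visit may reflect only part of the treatment. A time-to-response comparison that allows for interval censoring is a legitimate alternative.

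Finally, this is a 50-person pilot, for which a particular model is partly a matter of choice. That is fair, but it does not rescue within-arm tests: an estimated arm difference with its interval is what a small pilot can usefully provide.

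**Conclusion.** The point holds in a limited form. Speed and between-group time course sit in the hypothesis and principal aim alongside overall efficacy, and no valid inferential between-arm test of them is planned. The visit lists disagree beyond weeks 4 and 12.

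If conclusions were drawn from separate within-arm tests, two identical arms of 25 would give one significant and one non-significant result 29% to 50% of the time, for assumed standardized changes of 0.3 to 0.6.

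Averaging weeks 2, 4 and 6 lowers the variance to 52–61% of that for one adjusted visit, a gain in information of 1.65 to 1.9 times. A reader might round this up to a doubling, but it falls short of that and depends on the equal-correlation, equal-difference and no-dropout assumptions. Under the unequal-difference curves the gain is smaller still.

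**What to change.** 1. Reconcile the protocol and SAP schedules, state which visits were collected for each outcome, and explain any change.
2. Replace the baseline-versus-follow-up t-tests, and the protocol's paired t-test between groups, with one repeated-measures model per continuous outcome. Include arm, visit, arm-by-visit and baseline, and use every visit collected.
3. Report the between-arm difference with a 95% CI at each visit.
4. Pre-state one early contrast: the average over weeks 2, 4 and 6 if those visits were collected, otherwise the earliest visits held. Describe it as an early between-arm difference, not as a pure measure of speed. A single contrast also avoids separate unadjusted tests at each visit, whose family-wise error would reach 1 − 0.95⁴ = 18.5% for four visits or 1 − 0.95⁵ = 22.6% for five if independent.
5. Keep the responder percentages by arm and visit, labelled as descriptive.

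The cost is revised analysis text, one standard model per outcome and an account of the visits held. No extra subjects are needed. If weeks 2 and 6 were not collected they cannot be recovered, and the early contrast will rest on fewer visits and be less precise.
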